Hence, a primary concern of this study is to investigate the fundamental role of processing speed in enhancing cognitive and functional outcomes in the first episode psychosis. The potential of such interventions will be initiating as early as possible as the great potential in the early stage is promising. It is imperative for CR and enhancement from the trained skills that generalised the social functioning and job-related accordingly. It is evidently suggestive that the most feasible and realistic cognitive training should be adopted in reducing disability and to ameliorate functional recovery for its active ingredient to attain the treatment aims effectively (Bowie et al., 2008). The vigorous approach seems to have affirmative prognosis toward significant change in real-world functioning which manifest a holistic perspective in recovery process. This innovative neuropsychological model of remediation will be more robust with a well-articulated theoretical rationale and clearly understood, induce specific mechanisms of action that are grounded in the neuroscience of learning and cognition, robust, durable change and outcome measures with impactful metacognitive strategies in generalisation beyond the trained task that consequently bring a meaningful improvements of functional outcome. The adjunctive psychosocial interventions in CR may vividly elevate widespread gains in schizophrenia.

Therefore, a study of randomised controlled trial through adjunctive CR in ReMind program that focuses on the lower targeted deficit of Processing Speed is crucial to be conducted with the primary aim to evaluate the efficacy in patients with FEP in Klang valley, Malaysia to augment global cognition and functional outcomes. It is also promising to embrace metacognition through in enhancing cognitive performance and psychosocial for higher functioning via real-world recovery.

Research Objective

Primary objective:

To evaluate the efficacy of Cognitive Remediation to determine the efficacy of Cognitive Remediation in improving Processing Speed in patients with First Episode Psychosis

Specific Objectives:

- 1. To measure the psychosocial functions of First Episode Psychosis participants after intervention.
- 2. To compare the difference between psychopathology of First Episode Psychosis before and after intervention.
- 3. To explore the psychotic symptoms, significant changes and effect of functioning among the participants during pre and post intervention

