- 4. To evaluate the influence of Processing Speed to predict the cognitive outcome in First Episode Psychosis.
- 5. To assess the efficacy of Cognitive Remediation Therapy in enhancing global cognitive domains in First Episode Psychosis and functional outcomes.
- 6. To ascertain the role of processing speed as mediator in enhancing global cognitive domains.

Research Question

- 1. How is the psychosocial functions of First Episode Psychosis participants after intervention between conventional NEAR and REMIND treatment?
- 2. What is the difference between psychopathology of First Episode Psychosis before and after intervention?
- 3. Is there any correlation between improvements in cognitive impairment and functioning outcomes?
- 4. How do the interviews with first episode psychosis participants support the quantitative results that their cognitive functioning changes during the post intervention?
- 5. Is there any significant mean difference between Processing Speed in REMIND andother cognitive domains in conventional NEAR?
- 6. How does Processing Speed affect the cognitive outcome in First Episode Psychosis?
- 7. Is there any significant difference of efficacy towards cognitive domains performance between conventional NEAR and REMIND treatment?

Research Hypothesis

In the present study, the booster cognitive remediation therapy of processing speed (REMIND) will be examined whether it is superior to conventional treatment (NEAR) in improving cognitive functioning in first episode psychosis patients which the null hypothesis is no difference between the two intervention groups.

Conceptual Framework

The Neuropsychological Educational Approach to Rehabilitation (NEAR) Model

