This single-blinded randomised controlled trial will address the efficacy of CR therapy using NEAR model by targeting processing speed in first episode psychosis. Participants' cognition, functioning and clinical symptoms will be assessed at baseline and then randomised to treatment arm or standard care of CRT as active control for 15 sessions/ over 8 weeks. All participants will be assessed again at post-randomisation assessment with 3 months follow-up. A sequential mixed methods design is considered, in which intervention will be executed in sequence followed by in-depth interview before the data could be triangulated. There will be primary outcome of improvement in global cognition and psychosocial as secondary outcome. All procedures and reporting of primary and secondary outcomes will follow Consolidated Standards of Reporting Trials (CONSORT) 2010 guidelines.

The primary purpose of ReMind study will execute intervention of CR with the use of quantitative instruments to test the eclectic theories of neuropsychological, learning, educational psychology and rehabilitation psychology to predict the treatment effect between independent variables of additional Processing Speed in NEAR treatment and global cognitive domains and functional outcomes as dependent variables in patients with FEP.

Randomisation and Allocation Concealment

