The simplest formula for the sample size calculation were identified through continuous outcome and equal sample sizes in both groups yields (Noordzij et al., 2010), which primary outcome of this study, a priori between-group difference at 5 months with cognitive performance, BACS composite score. A difference in cognitive function of 30.6 between the treated and control group $(\mu 1-\mu 2)$ with the SD of 49.9 (Rodríguez-Sánchez, Crespo-Facorro, González-Blanch, Perez-Iglesias, & Vázquez-Barquero, 2007) is considered as clinically relevant and specified such an effect to be detected with power of 80% power (0.80) and a two-sided alpha of 0.05 and beta of 0.20. This requires 42 participants to be randomised to each arm. Assuming 20% of attrition rate, the adjusted sample size will be involved in this intervention programme is 52 participants each arm with 104 participants in total for achieving desired statistical significance for a given hypothesis.

Inclusion Criteria

The inclusion criteria is established to recruit clinically stable participants according to DSM-V criteria for schizophrenia, schizophreniform disorder or schizoaffective disorder as diagnosis and presenting with cognitive deficits of young adults between 18 to 40 years. They will be provided a written informed consent and fulfil the criteria of cognitive measures, symptomatology and other functioning which to be considered as participants in this study. Moreover, they should be able to understand and/or speak a Malay language, read and write in Malay and/or English as well as able to give informed consent as considerations for being a participant in this study.

Exclusion Criteria

Participant can be excluded if they have previous diagnosis of mental retardation, psychotic disorder related to a general medical conditions or substance-induced psychotic disorder as well as concurrently undergo other types of CRT. The participation in the study is voluntary and

participants are free to withdraw from the study at any time for any reason without consequences for treatment possibilities. The researcher may decide to terminate the study at any time. Participants will be informed if the study is terminated and follow-up visits will be arranged if needed. They may also be withdrawn from the study at any time at the discretion of the researcher.

Measures and Instruments

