The SCoRS is a rating scale that focuses on cognitive impairment and the degree to which it affects day-to-day functioning. It consists of a 20-item interview completed by both the patient and an informant. The items are rated on a 4-point ordinal severity scale. The interviewer then generated the ratings on all items based on the results of both interviews, which represented the best judgment of the patient's true impairment, after considering the patient and informant reports. Finally, the interviewer generated a global rating that is scaled on a 10-point scale (1–10). It helps clinicians evaluate the ties between cognitive impairment and poor functioning in both research settings and daily clinical practice. The SCoRS global ratings have been significantly correlated with psychosocial functioning and its functional capacity which is used as co-primary measures to predict real world functioning. It has excellent test-retest reliability, strong relation to cognitive performance, and proven sensitivity to treatment. Internal consistency for the scale was calculated by using Cronbach's alpha coefficient, which was found

to be 0.79 (Keefe, Poe, Walker, Kang, & Harvey, 2006).

Social Functioning Scale (SFS)

Social Functioning Scale (SFS) was adapted by which developed by Birchwood et al. (1990). The scale found to be useful for diagnosing deficits of the patients' functioning and for planning of the rehabilitation procedure. The scale consists of 76 items grouped into 7 domains which comprise of Social Engagement/Withdrawal, Interpersonal Behaviour, Prosocial Activities, Recreation/Pastimes, Independence-Performance, Independence-Competence, Employment/ Education. Total score of SFS ranges between 55 to 145 points. Scoring more than 115 points means good functioning. In this study, the SFS will be employed to examine real-world functional performance. The SFS will be asked to complete by the research team rather than self-rated by participant itself to obtain information on real-world performance (Bowie et al., 2008).

Schizophrenia Quality of Life Scale Revision 4 (SQLS-R4)

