The SQLS-R4 a fourth revision of the original SQLS developed by Wilkinson and colleagues in 2000. It measures two domains of psychosocial feelings, and cognition and vitality in individuals with a diagnosis of schizophrenia. It can be applied in clinical research and any publication due to its impressive measurement characteristics of this tool. In this study, the SQLS-R4 which has already translated into Malay version will be used to the respondents (Taha, Ibrahim, Rahman, Shafie, & Rahman, 2012).

Outcome measures

The trial involves the most effective treatment to enhance the outcomes in the early stages of psychosis with the primary aim to improve the long-term cognitive functioning.

Baseline measures

[figure not shown]
All inclusion criteria must be met before continuing neuropsychological assessment of the BACS-M to measure the primary outcome of cognitive functioning, PANSS which will be used to assess symptomatology and psychopathology of participants, SCoRS for functional capacity, SQLS-R4, and SFS for secondary outcomes of psychosocial functions.

Study Procedure

The study will involve multidisciplinary team, which covers from assessment, interview, randomisation and intervention. The CR training will be required team of trained clinicians

including Clinical Psychologists with at least a master's degree, Psychiatrists, Occupational Therapists, and Nurses as the recruitment and training team. In fact, the person involved in this study have been provided with a 2-day training on CR and its process to ensure the fidelity of treatment will be sustained with thorough supervision. All the assessments and interview will be administered prior to randomisation into intervention programme and immediately after intervention. It followed by interview sessions of psychopathology, psychosocial and quality of life to participants. The three months follow up is considered after termination prior to study analysis as shown in the diagram.

Consolidated Standards of Reporting Trials (CONSORT) flow diagram of participants through each stage of a randomized trial.

ReMind Cognitive Training

The intervention consists of 15 sessions with the selected web based computerised cognitive training associated with homework between each session. In this program, the therapy intensity involved 2 sessions per week for 8 weeks with 15 hours to deliver an adequate treatment to improve cognitive functioning (McGurk et al., 2007a).

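### The primary objective is processing speed, but the stated primary outcome and the sample size are the BACS composite at 5 months

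*Protocol*

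**What the plan says.** The protocol describes what the trial is meant to show in several places.

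- **Title and Research Objective (Primary objective):** the aim is "to determine the efficacy of Cognitive Remediation in improving Processing Speed in patients with First Episode Psychosis". Global cognitive domains come only as specific objective 5. Objective 6 casts processing speed as a mediator.
- **Research Hypothesis:** the new programme is to be tested for being "superior to conventional treatment (NEAR) in improving cognitive functioning in first episode psychosis patients". This refers to cognition generally, not to speed.
- **Study design:** "There will be primary outcome of improvement in global cognition and psychosocial as secondary outcome".
- **Sample size calculation:** the primary outcome is the "a priori between-group difference at 5 months with cognitive performance, BACS composite score".
- **Baseline measures:** the BACS-M measures the primary outcome of cognitive functioning. The remaining instruments follow, including "SCoRS for functional capacity, SQLS-R4, and SFS for secondary outcomes of psychosocial functions".
- **Functional Assessments and the SCoRS section:** the first reports a literature recommendation for a co-primary measure and then introduces SCoRS. The second speaks of psychosocial functioning and "functional capacity which is used as co-primary measures to predict real world functioning".

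The BACS section assigns three of the six subtests (verbal fluency, token motor, symbol coding) to processing speed. The other three cover verbal memory, working memory and executive function.

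**The concern.** A primary objective and a primary outcome should be the same question asked twice. Here they are different variables. The intervention trains processing speed, so speed is where a gain is most likely, while the composite also needs the untrained domains to move or at least not to dilute the gain. A result with better speed and a null composite is therefore quite possible. The primary objective would call it a positive trial; Study design, Sample size calculation and Baseline measures would call it negative.

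The confirmatory claim is at stake. If the conflict is left standing, the choice could be made once the results are known, with a passage to cite either way. Study design also promises CONSORT reporting of primary and secondary outcomes, which needs one identifiable primary. The SCoRS wording adds a smaller inconsistency of the same kind.

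**Working it through.** **1. Reproduce the plan's own figure.** Inputs from Sample size calculation: difference 30.6, SD 49.9, two-sided alpha 0.05, power 80%, equal arms, 20% attrition.

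- n per arm = 2 × [49.9 × (1.960 + 0.842) / 30.6]² = 41.7, so 42, as stated. The exact t-test version gives 42.7.
- Power at 42 per arm is 80.2%.
- With attrition, 42 / 0.8 = 52.5; the plan states 52. The rounding does not matter here.

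The sample size is coherent for one endpoint, the BACS composite, at alpha 0.05. None is stated for processing speed.

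**2. How far do speed and composite overlap?** Statistical Analysis describes the composite as an average of six z-scores. Take speed as the average of its three. The protocol gives no correlations, so assume a common correlation r between subtests.

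- Correlation of the two scores = 3(1 + 5r) / √[(6 + 30r)(3 + 6r)].
- At r = 0.4: 9 / √(18 × 5.4) = 0.913.
- At r = 0.2 it is 0.845; at r = 0.6, 0.954. With r = 0 it is 0.707.

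**3. False-positive rate if either score could be chosen after the fact.** With no treatment effect and each score tested two-sided at 0.05 at one visit, the chance that at least one is significant follows from the bivariate normal distribution:

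| Subtest r (assumed) | Speed–composite correlation | At least one p < 0.05 |
|---|---|---|
| 0 | 0.707 | 8.3% |
| 0.2 | 0.845 | 7.5% |
| 0.4 | 0.913 | 6.9% |
| 0.6 | 0.954 | 6.4% |

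A simulation with 42 per arm and r = 0.4 gives 6.8%, in agreement. For the composite alone the rate is 5%.

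**4. Can the two answers differ in practice?** As an illustration, suppose only the three speed subtests respond, each by the same amount.

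- The standardised effect on the composite is then √[(3 + 6r)/(6 + 30r)] times that on speed. At r = 0.4 this is √(5.4/18) = 0.548.
- Put the plan's standardised effect on speed: 30.6/49.9 = 0.613. The effect on the composite is 0.613 × 0.548 = 0.336.
- Power at 42 per arm is Φ(effect × √21 − 1.960): 80.2% for speed and about 34% for the composite.

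Under this scenario a significant speed result with a non-significant composite would be common. The scenario is an assumption, not a forecast.

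**5. SCoRS.** Functional Assessments and the SCoRS section use co-primary language. Baseline measures names the BACS-M for the primary outcome and lists SCoRS afterwards with the functional and secondary instruments. Study design makes psychosocial outcomes secondary. These statements do not agree.

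**The case against.** The strongest reply is that the protocol is consistent wherever it uses the term primary outcome for a variable: Study design, Sample size calculation and Baseline measures all point to cognition on the BACS, and the hypothesis agrees. Processing speed is mostly described as the target of the intervention. Study design makes it part of the independent variable, and objective 6 makes it a mediator. On that view the title describes the treatment, and only the primary objective sentence is out of line.

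Much of this stands. It limits the conflict to the primary objective (with the title behind it) against the outcome and sample-size sections. It does not remove it: the primary objective is the sentence that defines the trial's main claim, and it names speed while global cognition comes fifth among the specific objectives.

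A reader might infer more: that the protocol names three primary outcomes (speed, composite, SCoRS), and that the 5% error rate therefore fails. The text does not support this.

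- Only global cognition on the BACS is ever called the primary outcome.
- The SCoRS wording is largely a literature recommendation and a general description of the instrument.
- In the usual sense, co-primary means both must be significant. That costs power and does not raise the type I error.
- Rates of roughly 9% to 17% arise only if SCoRS, or also the post-treatment visit, may win on its own. The protocol states no such rule, and it fixes the primary comparison at 5 months.

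Nor is the lack of an ordering or alpha rule for secondary endpoints a fault here. That is commonly left to the statistical analysis plan, which is not at hand.

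**Conclusion.** The point holds in a limited form. The primary objective and the primary outcome are different variables, and the protocol lends support to either as the confirmatory result. The co-primary wording for SCoRS is a lesser inconsistency that should be cleared up at the same time.

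The size is modest on error rate and larger on interpretation. The 5% level is sound for the composite alone. It rises to about 7% only if speed or composite is chosen after seeing the data at one visit; that figure assumes equal subtest correlations near 0.4, with about 6.4% to 7.5% over 0.6 to 0.2. The greater consequence is that the protocol does not say how to judge a trial in which speed improves and the composite does not. This should be settled before analysis, since a later analysis plan would otherwise have to overrule one part of the protocol.

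**What to change.** State one primary endpoint everywhere: the between-arm difference in BACS-M composite at 5 months, on which the sample size is based. Then:

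- reword the primary objective and specific objective 5 so that global cognition on the BACS-M is the primary question;
- make processing speed a secondary outcome, optionally first in a fixed sequence and tested at 0.05 only if the composite is significant;
- call SCoRS secondary in Functional Assessments and in its own section, in line with Baseline measures.

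If the sponsor holds that processing speed is the primary question, keep the objective, change Study design, Sample size calculation and Baseline measures to match, and restate the sample-size basis for the speed score.

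The first route costs wording only: alpha stays at 0.05, 42 evaluable per arm still gives about 80% power under the plan's inputs, and no patients are added. Its downside is that a gain on processing speed alone could not be called the primary result.

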The randomisation will only be conducted after all the informed consent signed by the participants. The single blinded (masked) assessors will recruit the participants through demographic data and assessments. The blinding applies to ReMind training team involved in assessments, data management, data analysis, and drawing outcome conclusions except the patients and treatment providers which will not be blinded. A randomisation is performed, as the potential participants will be of the result of the process, which depends on two interrelated aspects; adequate generation of an unpredictable allocation sequence and concealment of that sequence until assignment occurs. The treatment allocation system will be set up so that the person enrolling participants does not know in advance which treatment the next person will get, a process termed allocation concealment (Douglas, Schulz, & Richard, 2014). The effective, accessible and straightforward method to conceal the randomization and maintaining allocation concealment that does not require the use of specialized technique will be using sequentially numbered, opaque sealed envelopes (SNOSE). Moreover, the methods are both reasonable to eliminate the source of bias.

Recruitment process and study population

Participants

A total of 104 participants who experienced a FEP will be assessed in cognitive and clinical assessments from Klang valley of Malaysia. There are in stable condition whether inpatients or outpatients from the psychiatric and mental health department at UKM Medical Centre, Kuala Lumpur Hospital, Kajang Hospital and Putrajaya Hospital.

Sample size calculation

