The descriptive statistics will be used to report the participants in terms of demographic and clinical data as well as inferential analysis such as t-test analysis for mean score of the post test. Hence, the Independent Sample t-tests will be used to compare participants and controls on age, years of education and premorbid IQ. The chi-square (χ 2) test will be used to compare the difference between groups in demographic characteristics. The relationship among the BACS measures will be evaluated through Pearson correlations among the composite scores by averaging all z-scores of the six primary measures. Pearson correlation for reliability and repeated measures for the validity of the test. The mixed model one-way analysis of variance (ANOVA) between and within group of intervention is expected to compare the difference between the means of pre and post treatment. The group differences on cognitive performance then analysed by the multivariate analysis of variance (MANOVA). The treatment effect on symptom and functioning outcomes will be analysed using Multiple Linear Regression (MLR) analysis. Effect sizes of the improvement in cognitive domain and psychosocial functioning will

also be calculated. The data analyses will be done using the SPSS version 22. All available data who met entry criteria will be analysed, which provided all outcomes on an intention to treat analysis (ITT) approach, assuming data which missing at random, including any significant predictors (Anaya et al., 2012).

Ethical Consideration

This study will be conducted in compliance with ethical principles outlined in the Declaration of Helsinki and Malaysian Good Clinical Practice Guideline. All potential participants will be enrolled in the study of cognitive remediation for first episode psychosis as defined in inclusion criteria. As the study involves UKM Medical Centre and government hospitals such as Kuala Lumpur Hospital, Kajang Hospital and Putrajaya Hospital, hence the approval from Ethics Committee of UKM and Ministry of Health (MOH) Malaysia ethical board (NMRR) have been obtained.

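### Four hospitals, but no blocking or stratification by hospital is specified, the number of envelope series is left open, and no named arm comparison includes hospital: a modest, cheaply avoided loss of precision

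*Protocol*

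**What the plan says.** The section on randomisation and allocation concealment asks for "adequate generation of an unpredictable allocation sequence and concealment of that sequence until assignment occurs" and then names the concealment device: the method "will be using sequentially numbered, opaque sealed envelopes (SNOSE". It mentions no blocks and no strata, and it does not say whether the envelopes form one central series or one per hospital.

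The Participants section draws patients "from the psychiatric and mental health department at UKM Medical Centre, Kuala Lumpur Hospital, Kajang Hospital and Putrajaya Hospital", with no recruitment target for any hospital.

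The Sample size calculation section uses a formula for a "continuous outcome and equal sample sizes in both groups" and arrives at 52 per arm, 104 in total, with no term for hospital.

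The Statistical Analysis section lists "inferential analysis such as t-test analysis for mean score of the post test", a mixed ANOVA, a MANOVA for cognitive performance, and multiple linear regression for symptoms and functioning. Hospital is named in none of them. The regression covariates are not listed. Predictors are mentioned only in the sentence on intention to treat and missing data.

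**The concern.** Hospital could plausibly matter here. The Study Procedure section describes delivery by teams of clinicians, patients may be inpatients or outpatients, and the programme includes group psychoeducation and bridging groups. If outcomes differ by hospital, a test without a hospital term leaves that variation in the error and widens the confidence interval. If the sequence is unrestricted, the arms can also be uneven within a hospital. That weakens the face validity of the realised comparison and, if groups are run by hospital and arm (the protocol does not say), may leave one arm short of members.

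Analysis covariates can be settled later. The allocation design cannot, because it has to exist before the first envelope is packed.

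**Working it through.** **Inputs from the protocol (Sample size calculation):** difference 30.6, SD 49.9, two-sided alpha 0.05, power 80%, 42 evaluable per arm, 20% attrition, 52 per arm.

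**Assumptions, not in the protocol:** simple 1:1 randomisation; 26 patients per hospital (104/4), with 44/30/20/10 as an unequal alternative; hospital share of outcome variance r from 0 to 20%.

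**1. The plan's own figure.** n per arm = 2(1.960 + 0.842)² × (49.9/30.6)² = 41.74, rounded up to 42, which matches the protocol. For attrition, 42/0.8 = 52.5, which rounds strictly to 53 against the stated 52. That difference is immaterial and not at issue here.

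**2. Imbalance under simple randomisation.**
- One hospital of 26, Binomial(26, 0.5): P(17:9 or worse) = 0.169. At least one of four: 1 − (1 − 0.169)⁴ = 52%.
- The same calculation for 16:10 or worse: 0.327 per hospital, 80% for at least one. For 18:8 or worse: 0.076 and 27%.
- With hospital sizes 44/30/20/10, by simulation, at least one hospital has 60% or more in one arm with probability 94%, and two-thirds or more with probability 49%.
- Whole trial, Binomial(104, 0.5): P(58:46 or worse) = 28%.

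**3. What unequal totals cost.** Standardised difference d = 30.6/49.9 = 0.613. Power comes from the noncentral t with noncentrality d × √(n₁n₂/(n₁ + n₂)) and 82 degrees of freedom, for 84 evaluable patients.
- 42:42 gives noncentrality 0.613 × √21 = 2.81 and power 79.3%.
- 47:37 (about the same ratio as 58:46) gives 78.7%.
- Averaged over all splits from simple randomisation: 78.8%.

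Lack of blocking alone therefore costs about half a point.

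**4. What leaving hospital out costs, taking 49.9 as the total SD.** With balanced arms and hospital in the model, the standardised difference becomes d/√(1 − r), with 84 − 5 = 79 degrees of freedom. Simulation shows that the unadjusted test under simple randomisation stays at about 79% for every r, so the 78.8% above serves as the reference.

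| Hospital share r (assumed) | Stratified and adjusted | Gain over 78.8% |
|---|---|---|
| 0 | 79.3% | 0.5 points |
| 5% | 81.3% | 2.5 points |
| 10% | 83.3% | 4.5 points |
| 20% | 87.4% | 8.6 points |

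Because blocking alone is worth about half a point, most of any gain comes from the hospital term.

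**5. If 49.9 is instead a within-hospital SD.** The protocol does not say which it is. The unadjusted SD would then be 49.9/√(1 − r). With the normal formula, which gives 80.2% at r = 0, unadjusted power at 42 per arm is 78.2%, 76.0% and 71.0% for r = 5%, 10% and 20%. Adjusting for hospital restores 80.2%, ignoring the 3 degrees of freedom.

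**The case against.** A reader might infer that allocation is a single unrestricted series across the four hospitals and that the analysis disregards hospital. The protocol supports neither statement. The envelope sentence concerns concealment, and sealed envelopes are equally compatible with blocked, hospital-specific series. The stated 52 per arm even hints that some restriction is intended. The Statistical Analysis section names families of tests without listing covariates, so hospital is neither included nor excluded, and covariates may properly be set in an analysis plan that is not at hand.

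A reader might also infer that a chance excess of one arm at one hospital confounds the treatment comparison. Under concealed randomisation it does not: the estimate is unbiased on average and the type I error is not inflated. The cost is precision.

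That cost is small at low hospital shares. The larger gains need 10% or 20% of variance to lie between hospitals. The protocol offers no evidence of that, and all four hospitals are in one region.

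All of this stands, and it limits the size of the point. It does not remove it: the randomisation section as written leaves open a design feature that must be fixed before enrolment, and the named tests, taken literally, are less efficient than an equally simple alternative.

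**Conclusion.** The point holds as a low-cost improvement to the plan; it does not threaten validity. For four hospitals the protocol specifies no blocking or stratification, leaves the number of envelope series open, names no hospital term in any arm comparison, and does not secure the equal arms used to size the trial.

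If it were followed literally with simple randomisation and unadjusted tests, the loss would be about 0.5 to 2.5 points of power for a hospital share of 0 to 5%, 4 to 5 points at 10%, and 8 to 9 points at 20%. Lopsided arms within at least one hospital would be likely. These sizes rest on the assumed variance shares and, for the imbalance figures, on the assumed recruitment per hospital. The sample-size arithmetic itself is not in dispute.

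**What to change.** In the randomisation section, specify four hospital-specific series of sequentially numbered, opaque sealed envelopes. Each should be generated in randomly permuted blocks of varying size. The block sizes should not be disclosed to recruiting or treating staff. Existing study personnel who take no part in recruitment should prepare the series. Since the protocol blinds assessment, data management and analysis, they should take no part in those either.

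In the Statistical Analysis section, include hospital as a fixed factor in every arm comparison. For the primary outcome, replace the plain post-test t-test with a linear model containing arm and hospital. The two changes belong together: stratifying without adjusting would balance the arms but leave hospital variation in the error term.

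Cost: four envelope series in place of one (if one was intended), 3 degrees of freedom, and a few sentences of protocol text. No extra patients or visits are needed. If hospital explains nothing, power is essentially unchanged (79.3% in either case with balanced arms). The one drawback is slight predictability at the end of a block, since treatment providers are not blinded; varying, undisclosed block sizes limit it.
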